4.5. Safety Analyses

The safety analyses will be based on the Safety Analysis Set, unless otherwise specified.

4.5.1. Definition of endpoint(s)

The definitions of an AE or Serious Adverse Event (SAE) can be found in Appendix 3 of the Protocol.

4.5.2. Adverse Event Analyses

Adverse events analyses including the analysis of adverse events (AEs), Serious AEs (SAEs) and other significant AEs will be based on GSK Core Data Standards.

Summary tables of AE and SAE will include both on-treatment and post-treatment data. That is AE and SAEs reported at any time post dose are summarized.

An overview summary of AEs, including counts and percentages of participants with any AE, AEs related to study intervention, AEs leading to permanent discontinuation of study intervention or withdrawal from study, SAEs, SAEs related to study intervention, fatal SAEs, and fatal SAEs related to study intervention will be produced.

Adverse events will be coded using the standard Medical Dictionary for Regulatory Affairs (MedDRA dictionary).

The frequency and percentage of AEs will be summarized in two ways: 1) in descending order by System Organ Class (SOC) and Preferred Term (PT) 2) in descending order by SOC, PT and Maximum Intensity.

Common ($\geq 3\%$) AEs will be summarized by overall frequency.

A separate summary will be provided for study intervention-related AEs. A study intervention-related AE is defined as an AE for which the investigator classifies the possible relationship to study intervention as “Yes”. The summary Table will be displayed in descending order by SOC and PT.

A worst-case scenario approach will be taken to handle missing relatedness data, i.e. the summary Table will include events with the relationship to study intervention as ‘Yes’ or missing

All SAEs will be tabulated based on the number and percentage of participants who experienced the event. Separate summaries will also be provided for study intervention-related SAEs. The summary Tables will be displayed in descending order by SOC and PT.

A study intervention-related SAE is defined as an SAE for which the investigator classifies the relationship to study intervention as “Yes”. The summary Table will be displayed in descending order by SOC and PT.

Adverse Events of Special Interest

Adverse events of special interest (AESI) for GSK3511294 program include:

- Allergic reactions including anaphylaxis

Note: these events will be assessed by the investigator as to whether they meet the diagnostic criteria for anaphylaxis as outlined by the 2006 Joint NIAID/FAAN Second Symposium on Anaphylaxis.

- Type III hypersensitivity (immune complex disease/vasculitis) reactions

- Local injection site reactions
- QTc prolongation

Summary tables of AESI will include both on-treatment and post-treatment data. That is AESIs reported at any time post dose are summarized.

AESI reported by the investigator as systemic reactions (further categorised by the investigator as either allergic [type I hypersensitivity] or other systemic reactions and assessed against Sampson criteria for anaphylaxis) are collected via targeted eCRF within the study. Vasculitis events and local injection site reactions are also collected via targeted eCRF within the study.

Separate summary Tables showing the number and percent of subjects with each type of AESI (excluding QTc prolongation) broken down by preferred term will be created.

For each type of AESI (excluding QTc prolongation) a profile summary Table will be produced containing information including, but not limited to, the number of occurrences of the event, event characteristics, time to onset, intensity, outcome and action taken.

Incidence, Relative Risk and Risk Difference SAE and AESI will be summarized.

AESI of QTc prolongation will be summarised as detailed in Section 4.5.6 ECG.

Adverse event data will also be summarised by ADA assay category result.

4.5.3. Laboratory Data

The haematology, clinical chemistry, urinalysis, and additional parameters to be tested are listed in Appendix 2 of the Protocol.

Summaries of laboratory data including chemistry and haematology parameters, and liver chemistry test data will be based on GSK Core Data Standards and unless otherwise specified will include on-treatment and post-treatment data.

Change from baseline for Chemistry and Haematology will be summarized.

Change from baseline for laboratory values will be summarized by visit.

Summary of worst-case laboratory results relative to PCI Criteria post-baseline relative to baseline will be done using categories of “To Low”, “To Within Range or No Change” or “To High”.

Summary of worst-case laboratory results relative to normal ranges post-baseline relative to baseline will be done using categories of “To Low”, “To Normal or No Change” or “To High”.

The derivation rule follows:

- Laboratory values will be classified as “Low”, “Normal”, or “High” based on the provided normal ranges.

Laboratory values will be classified as “Low”, “Within Range”, or “High” based on the provided PCI ranges.

- Change from baseline values will be classified relative to normal range as “To Low”, “To Normal or No Change”, or “To High”. Participants who do not change categories or move from out-of-range to normal will be classified as “To Normal or No Change”.

Change from baseline values will be classified relative to PCI ranges as “To Low”, “To Within Range or No Change”, or “To High”. Participants who do not change categories or move from out-of-range to normal will be classified as “To Within Range or No Change”.

- A “worst case post-baseline” change classification relative to normal ranges will be derived for each treatment in which participants will be counted in the “To Low” or “To High” categories if they reported a change from a “Normal” baseline to a value below or above the normal range, respectively, at any on-treatment scheduled, unscheduled, or early withdrawal visits. Participants who did not report a change to a value outside the normal range at any visit will be counted in the “To Normal or No Change” category.

A “worst case post-baseline” change classification relative to PCI Ranges will be derived for each treatment in which participants will be counted in the “To Low” or “To High” categories if they reported a change from a “Within Range” baseline to a value below or above the within range, respectively, at any on-treatment scheduled, unscheduled, or early withdrawal visits. Participants who did not report a change to a value outside the within range at any visit will be counted in the “To Within Range or No Change” category.

- Participants having both high and low values relative to normal ranges at post-baseline on-treatment visits for safety parameters will be counted in both the high and low categories of the “worst-case post-baseline” row of related summary tables.

Participants having both high and low values relative to PCI ranges at post-baseline on-treatment visits for safety parameters will be counted in both the high and low categories of the “worst-case post-baseline” row of related summary tables

A scatter plot of Maximum post-baseline vs Baseline for ALT and maximum post-baseline ALT vs maximum post-baseline total bilirubin will be produced. In addition, if any liver stopping or liver monitoring events occur during the study, summaries of liver

monitoring/stopping event reporting and hepatobiliary laboratory abnormalities will be produced.

Samples for anti-MPO antibody, anti-PR3 antibody, ANA, and anti-dsDNA antibody are collected at baseline visit and if clinically indicated post baseline, analysed on as needed basis and will be summarised only for participants with data available.

The details of the planned displays will be in OPS.

Hepatobiliary Laboratory Abnormalities will be summarized. Summary of Worst-Case Urinalysis Results (Discrete or Character Values) Post-Baseline Relative to Baseline will be summarised.

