6.2.5. Multiple measurements at One Analysis Time Point

Mean of the measurements (e.g., ECG) will be calculated and used in any derivation of summary statistics but if listed, all data will be presented.

If there are two values within a time window the value closest to the target day for that window will be used. If values are the same distance from the target, then the mean will be taken.

Participants having both High and Low values for Normal Ranges at any post-baseline visit (including post-baseline unscheduled assessments) for safety parameters will be counted in both the High and Low categories of “Any visit post-baseline” row of related summary tables. This will also be applicable to relevant Potential Clinical Importance summary tables.

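### The worst-case shift rule in SAP 4.5.3 leaves some Low-to-High and High-to-Low participants in no category, and counts others in the category they started in

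*SAP*

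**What the plan says.** SAP 4.5.3 (Laboratory Data) sets out the derivation as a list. Each rule is given for normal ranges and then again for PCI ranges.

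- **Value classes:** "Laboratory values will be classified as “Low”, “Normal”, or “High” based on the provided normal ranges". The PCI version uses Low, Within Range and High.
- **General change rule:** "Participants who do not change categories or move from out-of-range to normal will be classified as “To Normal or No Change". It sets no condition on baseline for 'To Low' or 'To High'.
- **Worst-case rule, out-of-range categories:** a participant enters 'To Low' or 'To High' "if they reported a change from a “Normal” baseline to a value below or above the normal range". The PCI version requires a Within Range baseline.
- **Worst-case rule, remaining category:** the sentence that fills 'To Normal or No Change' begins "Participants who did not report a change to a value outside the normal range at any visit will be counted in the", so entry requires that no change to an out-of-range value was reported. The PCI sentence, which fills 'To Within Range or No Change', sets the same condition.
- **Both-values rule:** participants with both high and low post-baseline values are counted in both categories of the worst-case row. SAP 6.2.5 has matching text that sends such participants to both categories: "Participants having both High and Low values for Normal Ranges at any post-baseline visit (including post-baseline unscheduled assessments) for safety parameters will be counted".

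SAP 4.5.5 (vital signs) and 4.5.6 (ECG) take over the PCI derivation by reference, as a similar rule.

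**The concern.** The two halves of the worst-case rule are not complements. One half is conditioned on where the participant started. The other is conditioned on whether any change to an out-of-range value was reported. A participant who starts out of range on one side and goes out of range on the other falls between them. These are the largest shifts a three-class table can show, and a worst-case row exists to display shifts of that kind.

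The general change rule and the worst-case rule also disagree on the same data. Two programmers following the SAP could place such a participant in 'To High', in 'No Change', or nowhere. The worst-case row could then show fewer shifts than the general rule implies, or its categories could fail to account for every participant.

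**Working it through.** **Classification check.** There are 3 baseline classes. The set of classes seen post-baseline is any non-empty subset of the three, so 2³ − 1 = 7 sets. This gives 3 × 7 = 21 patterns.

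A whole-range crossing is a Low baseline with High among the post-baseline classes (4 sets) or a High baseline with Low among them (4 sets), so 8 patterns. Applying the rules literally:

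| Baseline | Post-baseline classes | Worst-case rule alone | With both-values rule | General change rule, by exclusion |
|---|---|---|---|---|
| Low | High | none | none | To High |
| Low | High, Normal | none | none | To High |
| Low | High, Low | none | To Low and To High | To High |
| Low | High, Low, Normal | none | To Low and To High | To High |
| High | Low | none | none | To Low |
| High | Low, Normal | none | none | To Low |
| High | Low, High | none | To Low and To High | To Low |
| High | Low, High, Normal | none | To Low and To High | To Low |

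The other 21 − 8 = 13 patterns are all classified. The worst-case rule alone therefore misses 8 patterns, every one a crossing. The both-values rule picks up 4 and leaves 4 of 21 in no category. In the 4 it picks up, it adds a count in the participant's own baseline category, which is not a change.

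**How many participants.** The documents give no rate of crossing, so any count rests on assumptions. Those used here are:

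- 140 participants (SAP section 5, planned enrolment);
- standard normal values with a central-95% reference range, so limits at ±1.96;
- a baseline and 8 post-baseline values (assumed);
- a common within-subject correlation (assumed);
- 20 two-sided parameters (assumed).

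Expected number out of range at baseline, per parameter: 140 × 0.05 = 7. Monte Carlo results per parameter, then multiplied by 20:

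| Correlation | Crossers per parameter | Still unclassified after the both-values rule | Unclassified over 20 parameters |
|---|---|---|---|
| 0.2 | 0.35 | 0.30 | about 6 |
| 0.3 | 0.14 | 0.13 | about 2.5 |
| 0.5 | 0.01 | 0.01 | about 0.2 |

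Against 140 × 20 = 2,800 participant-parameter combinations, the top figure is 6 / 2,800, or about 0.2%.

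**PCI, vital-sign and ECG tables.** Several PCI limits in SAP 6.2.1 are one-sided (albumin, lymphocytes, neutrophils, the liver tests, QTcF, QT), so no crossing is possible. Where limits are two-sided they are wide. A crosser would have to go, for example, from potassium below 3 to above 5.5 mmol/L, or from systolic pressure below 85 to above 160 mmHg. The simulation does not cover these tables, and crossings in them should be rarer than in the normal-range tables.

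**The case against.** A reader might infer more than the text supports, in three ways.

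- **That every whole-range crosser is lost.** The both-values rule classifies half of the crossing patterns. By expected count it helps less: at a correlation of 0.2 it reduces 0.35 per parameter only to 0.30.
- **That SAP 6.2.5 independently contradicts the worst-case rule for one-directional crossers.** It does not. It addresses only participants with both High and Low values and agrees with the both-values rule in 4.5.3.
- **That the stated laboratory safety endpoint is compromised.** That endpoint is change from baseline at discrete time points. The separate by-visit summary serves it, and this rule does not touch that summary.

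The intended meaning can also be recovered from the general change rule. Display details are deferred to the Output and Programming Specification, and laboratory summaries follow the sponsor's data standards. Neither is available, so nobody can say from the SAP how the table will be programmed. In addition, protocol 5.1 requires overtly healthy participants and admits out-of-range laboratory values only with documented justification. Seven per parameter out of range at baseline may therefore be too many.

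All of this limits the impact. None of it removes the gap. The derivation is stated in the SAP itself, and as written it leaves 4 patterns unclassified and conflicts with the rule just before it.

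**Conclusion.** The point holds as a defect of classification logic, and that part needs no assumption. Read literally, SAP 4.5.3 puts 4 of 21 patterns in no category and counts 4 more in a category that is not a change, while the general change rule gives a single clear answer for all 8.

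The practical effect is small. It is confined to the descriptive worst-case row, mainly in the normal-range laboratory tables. The expected number of unclassified shifts runs from near zero (correlation 0.5) to about 6 (correlation 0.2). That range depends on the assumed correlation, number of visits, number of parameters and share out of range at baseline. The primary PK analysis, the adverse event tables and the by-visit change-from-baseline summaries are unaffected. The correction is worth making because it is cheap and removes a contradiction, not because many participants are expected to be misplaced.

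**What to change.** In both worst-case rules of SAP 4.5.3 (normal-range and PCI):

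1. Define 'To Low' as any post-baseline Low value in a participant whose baseline was not Low, and 'To High' as any post-baseline High value in a participant whose baseline was not High.
2. Put all other participants in 'To Normal or No Change' ('To Within Range or No Change' for PCI).
3. Make the both-values rules in 4.5.3 subject to the same definition, so that nobody is counted in the category they started in. Do the same for the text in 6.2.5 wherever it feeds the change-classification row. A row that only records whether High or Low values occurred needs no baseline condition.

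Changing the worst-case rules alone would leave them in conflict with the both-values rules. With all three steps, all 21 patterns are classified and the 13 already classified by the worst-case rule do not move. Low to High becomes 'To High' only, and High to Low becomes 'To Low' only. The wording carries to 4.5.5 and 4.5.6 through their existing references.

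The cost is a sentence in each affected rule and one programming condition. No new data are needed.

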4.5.4. Complement (C3 and C4)

Test results for Complement (C3 and C4) will be included within the laboratory data transfer and summarised by parameter and visit and presented as a table and as a figure. The summary table will include baseline concentration, concentrations at each visit and ratio to baseline at each visit. Summary statistics to be presented are n, geometric mean, standard deviation (on log scale), median, minimum and maximum.

4.5.5. Vital Signs

Change from baseline for vital signs of Systolic Blood Pressure, Diastolic Blood Pressure, Heart Rate, Temperature, and Respiration Rate will be summarized.

Change from baseline for vital signs values of Systolic Blood Pressure, Diastolic Blood Pressure, and Heart Rate will also be summarized by worst-case post-baseline relative to PCI ranges using categories of “To Low”, “To Within Range or No Change”, or “To High”. The derivation rule is similar to those mentioned for PCI criteria of Laboratory Data (Section 4.5.3) and the classification (PCI ranges) is based on the following potential clinical importance specified in Section 6.2.1.3.

4.5.6. ECG

A summary of the change from baseline in each ECG parameter by visit will be provided. When triplicate ECG assessments are taken, mean of the measurement will be calculated first and summary statistics will be based on the calculated mean. This will apply to baseline assessments.

A summary of the number and percentage of subjects who had normal and abnormal ECG findings will be displayed by scheduled visits. Abnormal will include sub-categories of Clinically significant and non-clinically significant according to eCRF classification. When multiple ECGs were performed at the same planned timepoint, the worst-case finding will be summarized, except at baseline mean of triplicate baseline assessments will be taken.

If multiple meet criteria of worst case, then take the earliest.

Change from baseline for ECG parameters will be summarized by worst-case post-baseline relative to PCI Criteria using categories of “To Low”, “To Within Range or No Change”, or “To High”. The derivation rule is similar to those of PCI criteria of the Laboratory Data (Section 4.5.3) and the classification(PCI ranges)is based on the potential clinical importance specified in Section 6.2.1.2

Individual maximum QTcF values will also be summarised to show the number of subjects with maximum values (msec) that increased to the following categories: Decrease, no change or increase to ≤ 450 , increase to $450 < \text{to} \leq 480$, increase to $480 < \text{to} \leq 500$, increase to $500 < \text{to} \leq 530$ and increase to > 530 . QT uncorrected values will be summarised to show the number of subjects with maximum values in the following categories: <600 and ≥ 600 .

Additionally, individual maximum changes from baseline in QTcF values will be summarised to show the number of subjects with maximum changes (msec) in the categories: increase of ≤ 30 , increase of 31 to 60 and increase of > 60 .

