7.1.2. QTc Stopping Criteria

Since this is a single dose study, QTc stopping criteria do not apply.

A detailed assessment including a concomitant assessment for PK, renal chemistry and electrolytes (potassium, calcium, and magnesium), toxicology screen, and clinical evaluation (e.g., continuous cardiac monitoring, admission for direct observation or referral) and discussion with the medical monitor will be triggered in the following scenarios:

Refer for appropriate monitoring and treatment as per local protocol:

- Arrhythmia or evidence of clinical impact e.g., syncope.
- QTcF change from baseline > 60 msec and no clinical impact. (Baseline is the average of triplicate readings at pre-dose on Day 1).
- QTcF > 500 msec or uncorrected QT > 600 msec and no clinical impact.

Note: the QTcF should be based on averaged QTcF values of triplicate ECGs obtained over a brief (up to 10 minutes) recording period.

7.1.3. Criteria for Follow-up of Potential Type III Hypersensitivity (Immune Complex Disease/Vasculitis)

Due to the adverse findings of arterial inflammation that were observed in the 1-month, but not the 6-month, non-clinical toxicology studies, events potentially representing Type III hypersensitivity/immune complex disease/vasculitis should be promptly reported to GSK, and consultation with the medical monitor is encouraged. Treatment for the event will be given as medically required. If possible, PK, ADA, C3, and C4 samples may be taken at the time of the event along with hematology, clinical chemistry and urinalysis samples.

Symptoms potentially suggestive of vasculitis include but are not limited to:

- persistent* fever
- persistent* muscle and joint pain
- persistent* rash
- persistent* fatigue
- symptoms of peripheral neuropathy, such as numbness or weakness
- laboratory abnormalities, e.g., decreased platelet counts, elevated creatinine, decrease in complement C3/C4, abnormal urinary albumin/creatinine ratio

Note: *where persistent is considered to be a duration of ≥ 2 days

Participants who experience any of the above events should be monitored until the event resolves and/or a diagnosis is established.

The symptoms and clinical features are often non-specific and heterogenous with respect to the time course over which they develop, organ involvement, and the constellation of symptoms and severity. Early recognition of potential events of vasculitis is important for timely diagnosis and subsequent treatment.

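### Three rules in SAP 4.5.6 are wrong as written: the QTcF-change classes leave a gap between 30 and 31 msec, the QT cut at 600 msec conflicts with two other sections, and a categorical baseline finding is given a mean (minor)

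*SAP*

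**What the plan says.** SAP 4.5.6 groups each participant's maximum QTcF change from baseline as "increase of ≤ 30", "increase of 31 to 60 and increase of > 60" msec. SAP 4.1.1 defines the ECG baseline as the mean of the pre-dose triplicate. The protocol (schedule of activities and 8.3.3) makes post-dose ECGs single readings, apart from the exceptions in 7.1.2.

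For uncorrected QT, SAP 4.5.6 states that "QT uncorrected values will be summarised to show the number of subjects with maximum values in the following categories": below 600, and 600 or above. Protocol 7.1.2 lists as a trigger "QTcF > 500 msec or uncorrected QT > 600 msec and no clinical impact", and the table in SAP 6.2.1.2 also flags QT only above 600 msec.

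SAP 4.5.6 also counts participants with normal and abnormal ECG findings: "Abnormal will include sub-categories of Clinically significant and non-clinically significant according to eCRF classification". Where several ECGs share a planned time point, the worst finding is used, "except at baseline mean of triplicate baseline assessments will be taken".

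The section carries weight because SAP 4.5.2 leaves QTc prolongation out of the other tables dedicated to events of special interest and says: "AESI of QTc prolongation will be summarised as detailed in Section 4.5.6 ECG".

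**The concern.** Classes for a continuous quantity should give every value exactly one place. Here the baseline is a mean of three, so changes need not be whole numbers, and the strip between 30 and 31 msec belongs to no class. Anyone who falls there has an increase above 30 msec. The omission therefore works in one direction: the number above 30 msec can be too low, never too high, and the rows would not add up to the number assessed.

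The QT table can disagree with the other two places at exactly 600 msec.

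The baseline row of the findings table has no usable definition if a finding is recorded for each tracing. A programmer would have to choose a substitute, and the choice changes the row against which post-dose abnormalities are read.

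**Working it through.** SAP 4.5.6 gives no computed figure to reproduce, so the check passes values through the rules as written.

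**QTcF-change classes**

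Inputs: the baseline is a mean of three (SAP 4.1.1), post-dose readings are single (protocol 8.3.3), and the classes are those in SAP 4.5.6. Assumption: the machine reports QTcF in whole msec, which the documents do not say.

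The mean of three whole numbers ends in .00, .33 or .67. Enumerating all triplicates from 395 to 424 msec gives each ending a share of 1/3, so about 2/3 of changes are not whole numbers.

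| Baseline triplicate | Mean | Post-dose | Change | Class |
|---|---|---|---|---|
| 410, 411, 411 | 410.67 | 441 | 30.33 | none |
| 410, 410, 411 | 410.33 | 441 | 30.67 | none |

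There is no gap at 60: changes of 60.33 and 60.67 both fall in the class above 60. The absolute QTcF classes in the same section meet at 450, 480, 500 and 530 msec and leave no gap either.

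To size the gap, the maximum of six single post-dose ECGs (24 h, 48 h, Days 8, 15, 85 and 183) was simulated for 400,000 participants per setting, with no drug effect. The within-participant SDs are assumptions. Each was split equally between session and tracing for the baseline triplicate. Counts are scaled to the planned enrolment of 140.

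| Assumed SD (msec) | In the gap | Expected of 140 | Chance of at least one | Above 30 msec | Share of those lost |
|---|---|---|---|---|---|
| 8 | 0.17% | 0.24 | 21% | 0.9% | 19% |
| 10 | 0.59% | 0.82 | 56% | 4.8% | 12% |
| 12 | 0.98% | 1.37 | 75% | 11.4% | 9% |
| 15 | 1.28% | 1.79 | 83% | 23.2% | 5% |

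The count and the share lost move in opposite directions. The 19% loss belongs to a setting where only about 1.3 of 140 participants exceed 30 msec (140 × 0.0092).

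Two repairs are possible, and they differ. Contiguous classes on the unrounded change put 30.33 and 30.67 both in the middle class. Rounding first sends 30.33 to 30 (lowest class) and 30.67 to 31 (middle class). It would also turn 60.33 into 60 and so take it out of the class above 60.

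**Uncorrected QT**

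A maximum of exactly 600 msec is in the upper group under SAP 4.5.6 and unflagged under protocol 7.1.2 and SAP 6.2.1.2. All other values are treated alike. By Fridericia's formula, RR = (QT/QTcF)³. A QT of 600 with a QTcF of 500 needs RR = 1.2³ = 1.728 s, or 60/1.728 = about 35 beats per minute, so the case will be rare.

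**Baseline finding**

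The mean rule for interval values already stands in the first paragraph of 4.5.6, in 4.1.1 and in 6.2.5. The exception in the findings paragraph is attached to the categorical finding, for which a mean is undefined. As an illustration, suppose each tracing is abnormal with probability 10% (assumed). Using one tracing gives 10% abnormal at baseline. Using the worst of three independent tracings gives 1 − 0.9³ = 27.1%. Protocol 8.3.3 puts the tracings no more than 2 minutes apart, so independence is unlikely and 27% is an upper extreme.

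**The case against.** A reader might infer that the ECG section as a whole cannot be applied. The documents do not support that. The by-visit change from baseline, the table against the clinical-importance limits, the absolute QTcF classes and the class above 60 msec can all be run.

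A reader might also take the understated count as certain. It is conditional: it needs whole-msec readings and an unrounded change. The label for the middle class can be read as whole msec, and with rounding the gap closes. SAP section 1 defers data-handling conventions to a programming specification that was not available, and it may settle the matter. On the assumed SDs there is a 17% to 79% chance that nobody is affected, and an unclassified participant would show up when the rows failed to sum.

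No protocol trigger or clinical-importance limit sits at 30 msec. Protocol 7.1.2 uses a change above 60, and SAP 6.2.1.2 uses an increase above 60 and an absolute QTcF above 450.

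On the baseline finding, it would go too far to say that every participant is affected. The classification comes from the eCRF, which is not shown. If it holds one overall interpretation per triplicate, nothing needs combining.

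These points limit the size and certainty of the concern. They do not remove it. No rounding rule appears in the SAP or protocol, 4.5.6 does not refer to the programming specification for these rules, and no convention gives a mean of categories a meaning.

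**Conclusion.** The concern holds for three specific rules, and its severity is minor. The change classes are not contiguous, and the likely effect is about 0 to 2 of 140 participants without a class, all with increases just above 30 msec. That size rests on whole-msec readings, no rounding and assumed SDs of 8 to 15 msec. The QT boundary is a plain inconsistency at a single value. The baseline rule for findings is undefined wherever the eCRF records a finding per tracing; its effect cannot be sized from the documents. The consequences stay within descriptive safety displays, including the one dedicated to the QTc event of special interest. The primary comparison of Cmax and AUC(0-inf) does not depend on any of this.

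**What to change.** In SAP 4.5.6:

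1. Set the QTcF-change classes to ≤30, >30 to ≤60 and >60 msec, and state that they apply to the unrounded change. This matches the contiguous form of the absolute QTcF classes in the same section.
2. Reconcile the uncorrected-QT split with protocol 7.1.2 and SAP 6.2.1.2, so that exactly 600 msec is treated the same way in all three places.
3. Limit the triplicate mean to interval values, and state a categorical rule for the baseline finding where the eCRF records one per tracing. The worst case, as at other visits, is one option. If it is chosen, add a footnote that baseline rests on three tracings and post-dose visits usually on one, because this can make baseline look slightly more abnormal and mask some new findings.

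The cost is SAP wording and matching programming specifications. No data collection, visit or sample size changes.
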